9.7 Score validation

9.7.1 Reliability

With the correlation coefficient $\rho = 0.80$, a minimum value of the desired correlation coefficient $\rho_0 = 0.50$, a number of observations $k = 2$, $\alpha = 0.05$ and $\beta = 0.20$, the critical value for α from the normal distribution is 1.645 and the critical value for β from the normal distribution is 0.842. It is necessary to include 20 patients.

The study of inter and intra-examiner reproducibility will be evaluated with the Kappa coefficient. (64)

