7.2 Practical details of the ultrasound examination

The examination, the details of which can be found in **Appendix 4**, is carried out using a Sonoscape Expert 2 ultrasound scanner (Digital Color Doppler Ultrasound System; Sonoscape medical corp. China) equipped with a linear probe (7-10 MHZ) and a convex probe (3-5 MHZ). Both probes will be used for each of the swallowing trials.

In order to assess inter- and intra-examiner reliability, the tests will be performed by two different operators and twice by the same operator, i.e. 3 identical examinations in total, in the first 20 patients included.

The duration of an examination will not exceed 15 minutes, i.e. a total duration of the ultrasound examination of 45 minutes for the first 20 patients (15 minutes for examination, 3 examinations).

The patient is in a sitting position and performs salivary swallowing attempts on request of the operator.

The convex probe will be placed under the chin, in the sagittal plane and between the edges of the hyoid bone and the mandible. The acoustic shadows of these bones will allow us to localise the structures and centre the image. (53)(54)

The following elements will be assessed:

- The position of the hyoid bone at rest and during swallowing;
- The thickness of the geniohyoid at rest and during swallowing;
- The contractility of the tongue ;
- The duration of contraction of the geniohyoid ;
- The number of swallowing attempts.

The linear probe will also be placed submentally, along a transverse axis, in order to qualitatively and quantitatively evaluate the suprahyoid muscles (55)

Qualitative analysis will be performed using the Heckmatt Score. (56) Quantitative analysis will be performed by measuring the thickness of the muscles at rest and during contraction. These two measurements will be used to calculate its thickening fraction. The thickness of the muscle is calculated by quantifying the distance between the upper and lower fascia of the muscle.

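### The inputs stated in section 9.7.1 do not give 20 patients for the reliability study: the matching ICC formula gives 22, and 20 patients give about 76-77% power for that test, not the 80% that beta = 0.20 implies

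*Combined protocol and SAP*

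**What the plan says.** Section 9.7.1 (Reliability) of the combined protocol and SAP lists its inputs: expected correlation coefficient 0.80, minimum desired coefficient 0.50, k = 2 observations, alpha 0.05 and beta 0.20. It adds that "the critical value for α from the normal distribution is 1.645" and that the value for beta "from the normal distribution is 0.842". It concludes: "It is necessary to include 20 patients". It names no formula and states no allowance for losses. The 80% power is not written out; it follows from beta = 0.20.

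Section 7.2 puts the number into practice. Two operators scan the patient and one of them scans twice, three examinations in all, "in the first 20 patients included". Each examination takes at most 15 minutes.

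For the analysis, section 9.7.1 plans Kappa for both inter- and intra-examiner reproducibility. Section 9.2 assigns Bland-Altman to agreement between quantitative variables and Kappa to agreement between qualitative ones. Neither section plans an ICC.

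**The concern.** An expected coefficient, a minimum coefficient, a number of observations per patient and two normal quantiles are enough to fix a sample size. Put into the formula they appear to belong to, they do not return 20. A required size is also normally rounded up, and the nearest result to 20 (20.5) reaches it only by rounding down.

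Reliability is part of the research hypothesis (section 1.4) and of every secondary objective (section 2.2), and this subset is the only planned source of repeat scans. If 20 patients do not deliver the stated beta, the protocol overstates the chance of showing reliability above 0.50. The coefficient that was sized is also not one that the analysis sections plan to estimate.

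**Working it through.** **Inputs (all from section 9.7.1):** ρ1 = 0.80, ρ0 = 0.50, k = 2, z for alpha = 1.645 (one-sided 5%), z for beta = 0.842. The value k = 2 fits section 7.2: three examinations give one between-operator pair and one within-operator pair.

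**Formula (assumed, since none is named).** For testing an ICC against a minimum value:

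- θ = ρ / (1 − ρ), so θ0 = 0.50/0.50 = 1 and θ1 = 0.80/0.20 = 4
- C = (1 + kθ0) / (1 + kθ1) = (1 + 2) / (1 + 8) = 1/3
- n = 1 + 2 (z_alpha + z_beta)² k / [(ln C)² (k − 1)]

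**Plan's own figure.** The main term is 2 × (1.645 + 0.842)² × 2 / (ln 1/3)² = 4 × 6.185 / 1.207 = 20.5. Without the +1, and rounded down, this is the stated 20. That is a plausible origin, but the protocol does not confirm it.

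**Full formula.** n = 1 + 20.5 = 21.5, so 22.

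**Power at 20 by the same formula.** √(19 × 1.207 / 4) − 1.645 = 0.749, which corresponds to 77.3%.

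**Exact F tests.** Power is P(F > C × F0.95), with degrees of freedom (n − 1, n) for the one-way model and (n − 1, n − 1) for the two-way model when k = 2.

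| Patients | ICC formula | Exact one-way F | Exact two-way F |
|---|---|---|---|
| 20 | 77.3% | 76.8% | 75.7% |
| 22 | 80.8% | 80.4% | 79.5% |
| 23 | 82.4% | 82.0% | 81.1% |

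**Other formulas, because none is named:**

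| Method | Required n | Rounded up | Power at 20 |
|---|---|---|---|
| ICC formula without +1 | 20.5 | 21 | 79.1% |
| Fisher z for an ICC | 22.0 | 22 | 76.4% |
| Fisher z for a Pearson correlation | 23.5 | 24 | 73.2% |

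A two-sided alpha would give 27.0 before rounding up, but the stated 1.645 rules that reading out. None of the versions tried reaches 80% power with 20 patients.

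**The case against.** The strongest reply is that the protocol names no formula and speaks only of a correlation coefficient. The ICC formula is therefore an inference, and 20 is close to a recognisable result: 20.5 for the main term, with 79.1% power on that version. This stands as a reason not to call the figure a proven arithmetic error. It does not rescue 20, because that version still rounds up to 21 and still falls short of 80%.

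A second reply is that the gap is trivial beside the uncertainty in the planning values, which section 9.7.1 does not justify. This is fair. With the full formula, an expected 0.78 gives θ1 = 3.545, C = 3/8.091 = 0.371 and n = 1 + 24.74/0.984 = 26.1. An expected 0.82 gives θ1 = 4.556, C = 3/10.111 = 0.297 and n = 1 + 24.74/1.476 = 17.8. A shift of 0.02 moves the size by more than the two patients at issue. That bears on how serious the point is. It does not alter what the stated inputs give.

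A third reply is that 77% is not the power of the planned analysis either, because section 9.7.1 plans Kappa and specifies no test against 0.50. This also stands. A reader might infer that 20 is too few for the planned Kappa analysis and that 22 would be enough. The documents support neither inference, since they give no Kappa-based calculation. A reader might also infer that the main result is weakened. It is not: reproducibility is a secondary outcome (section 3.2), and the 100 patients are derived separately in section 9.1.

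**Conclusion.** The point is minor, and the protocol is wrong as written. The inputs in section 9.7.1 do not give 20 patients. The formula that best matches them gives 22, and the most favourable version gives 21. With 20 patients the power for an ICC test against 0.50 is about 76-77%, so the type II error is about 23-24% and not 20%. The shortfall is about two patients and three to four power points.

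This rests on reading the coefficient as an ICC tested one-sided at 5%, on the stated 0.80 and 0.50, and on all 20 patients contributing complete repeat scans. Across the other formulas tried, power at 20 runs from 73.2% to 79.1%. The move to 22 should not be oversold: under the exact two-way model, a natural choice with two operators, it gives 79.5%, and 23 are needed to pass 80%. All these figures apply to the ICC and not to Kappa.

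**What to change.** In section 9.7.1, name the formula and the ICC model, then choose one of two courses:

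- Keep 20 patients and state the power as about 76-77%. This costs one sentence.
- Do the repeat scans in the first 22 of the 100 patients already planned, or the first 23 if the two-way model is to reach 80%, and change section 7.2 to match. Each added patient has two extra scans of at most 15 minutes: four scans and at most 60 minutes in total for 22, six scans and at most 90 minutes for 23. No extra enrolment is needed.

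Under either course, align the analysis with the sizing. For the continuous measurements, report the ICC with its one-sided 95% lower bound against 0.50, alongside the Bland-Altman analysis in section 9.2. Keep Kappa for the categorical items. State that the power figure refers to the ICC and that no power is claimed for Kappa. This adds one analysis and needs no further data.

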9.2 General aspects

Descriptive statistics will be based on means (+/- standard deviation) or medians [minimum-maximum] depending on the distribution of quantitative variables. Qualitative variables will be described in terms of numbers and percentages. Univariate comparisons will use the usual statistical tests after verification of the distribution of the variables (Chi2 or Fisher's test, t-test, anova or their non-parametric equivalents Wilcoxon and Kruskal-Wallis tests).

The tests will be performed at the 5% significance level. The 95% confidence intervals will be provided for each estimate.

Measures of association between quantitative variables will be made using Pearson's or Spearman's correlation coefficients depending on the distribution of the data. Measures of association between qualitative variables will be performed using the Chi-square or Fisher test depending on the distribution of the data.

The agreement between quantitative variables will be evaluated using the Bland-Altman method and that between qualitative variables using the Kappa coefficient.

Calculations will be made using IBM SPSS v21 and R software (version 3.6.1, www.R-project.org).

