9.3 Potential variables of the ultrasound score

Structures assessed		Results	Weighting
Language			
	Abnormal movement	Yes/No	
	> 1 attempt identified	Yes/No	
	Range of motion	< threshold > threshold (only to be defined)	
	Thickness	< threshold > threshold (threshold to be defined)	
Suprahyoid muscles			
	Signal strength (Heckmatt score)	1-4	
	Poorly defined fat involution and muscle boundaries	Yes/No	
	Decreased surface area compared to contralateral	Surface < threshold (threshold to be defined)	
	Thickening fraction compared to contralateral	< threshold > threshold (only to be defined)	
Geniohyoid			
	Decreased thickening fraction	< threshold > threshold (only to be defined)	
Laryngeal ascension			
	Ascension measured indirectly by assessment of hyoid bone ascension	< threshold > threshold (only to be defined)	

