9.4 Determination of classes and thresholds of quantitative variables

The hypothesis of a linear relationship between the logit of the diagnosis of swallowing disorders objectified by VFSS and the quantitative variable will be tested. If it is verified, the variable will be dichotomised. The threshold used will be determined using ROC (Receiver

Operating Characteristic) curve analysis, which will allow the threshold for which sensitivity and specificity are maximum to be retained. (62)

The variables for which the hypothesis is not verified will be split into classes. (63)

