9.7.2 Validity

The threshold of the ultrasound score defining the presence of swallowing disorders will be determined using Receiver Operating Characteristic (ROC) curve analysis.

Sensitivities, specificities, positive and negative predictive values and the diagnostic Odd ratio will be calculated to determine the diagnostic accuracy of the score.

10 Expected results in terms of scientific and professional advances

This study will allow the construction and evaluation of the reliability and validity of a new ultrasound score in the diagnosis of swallowing disorders. To our knowledge, no study has evaluated the performance of an ultrasound score in the diagnosis of swallowing disorders.

The analysis of the different structures involved in swallowing will also provide knowledge on the impairment of the functions and structures involved in swallowing. This may allow to better orientate the therapeutic strategy, both medical and rehabilitation.

Moreover, as the ultrasound examination is non-invasive, non-irradiating, can be performed in a simple consultation room and requires minimal cooperation from the patient, it could be an alternative to videofluoroscopy, currently the reference examination.

Swallowing ultrasound could thus also be a tool for monitoring the effectiveness of the treatments implemented, since it can be performed frequently without adverse effects.

The results of this study will only be applicable to a population of patients consulting a day hospital for suspected swallowing disorders, mostly related to ENT surgery or a prolonged stay in an intensive care unit. Further multicentre work and in other population categories to improve external validity.

11 Expected benefits and risks for patients

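### Section 9.7.1 sizes the 20 reliability patients on a correlation test (0.80 against 0.50, beta 0.20) that no planned analysis carries out

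*Combined protocol and SAP*

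**What the plan says.** Section 9.7.1 has two parts. The first is a sample size. An expected correlation coefficient of 0.80 is set against 0.50, described as "a minimum value of the desired correlation coefficient", with k = 2 observations, alpha 0.05 (critical value 1.645) and beta 0.20 (critical value 0.842). It concludes: "It is necessary to include 20 patients". Section 7.2 puts this into practice. The first 20 patients have three examinations, from two operators, one of whom examines twice, so each inter- or intra-examiner comparison has two examinations per patient.

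The second part is the analysis: "The study of inter and intra-examiner reproducibility will be evaluated with the Kappa coefficient". The synopsis repeats this. Section 9.2 gives a general rule: "The agreement between quantitative variables will be evaluated using the Bland-Altman method and that between qualitative variables using the Kappa coefficient". It also lists Pearson and Spearman coefficients, but for association.

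Other sections turn the measurements into categories. Section 9.3 lists the candidate items as yes/no signs, values below or above a threshold, and a four-level Heckmatt grade. Section 9.4 says of a quantitative variable that is linear in the logit: "If it is verified, the variable will be dichotomised". Of the rest it says: "The variables for which the hypothesis is not verified will be split into classes". Under Section 9.7.2 the score itself receives a ROC-based cut-off.

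No section names an ICC or plans to test any reliability coefficient against 0.50.

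**The concern.** A sample size with a stated beta is a claim about one particular test. Here the calculation is worded for a correlation coefficient with a null value of 0.50. The sentence that follows it evaluates Kappa, and Bland-Altman estimates limits of agreement and has no null value of 0.50. A reader would credit the reliability sub-study with 80% power, yet nothing in the plan has that power.

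Reproducibility is part of every secondary outcome in Section 3.2 and of the hypothesis in Section 1.4, and the sponsor expects excellent reliability. If the 20 patients are later defended by the calculation in 9.7.1, the defence would not apply to the results reported.

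**Working it through.** **1. Reproducing the 20.** Inputs from 9.7.1: rho = 0.80, rho0 = 0.50, k = 2, z = 1.645 (one-sided; two-sided would be 1.960) and z = 0.842.

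ICC test (Walter-Eliasziw-Donner approximation), with theta = rho/(1 − rho):
- theta0 = 0.50/0.50 = 1 and theta1 = 0.80/0.20 = 4
- C0 = (1 + 2×1)/(1 + 2×4) = 1/3, so (ln C0)² = 1.207
- N = 1 + 2k(1.645 + 0.842)²/[(k − 1)(ln C0)²] = 1 + 4×6.185/1.207 = 21.5, or 20.5 without the leading 1

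Pearson correlation (Fisher z), one-sided:
- N = 3 + (2.487/0.5493)² = 23.5, so 24

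The two-sided versions give 28 (ICC) and 30 (Pearson). The one-sided ICC test is the closest complete formula, at 21 to 22 patients. Without their additive constants the ICC and Pearson formulas both give 20.5, so closeness to 20 does not settle the matter. The stronger sign is that k = 2 is an input, because k has no place in a Pearson calculation.

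**2. Power of the ICC test with 20 patients**, 0.80 against 0.50, one-sided 5%:
- Approximation: Phi(√(19×1.207/4) − 1.645) = Phi(0.749) = 77.3%
- Exact F test, one-way ICC: 76.8%
- Exact F test, two-way consistency: 75.7%
- Simulation (40,000 runs), lower bound of the two-way absolute-agreement ICC with no systematic operator difference: 75.3%

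**3. Kappa on a yes/no or dichotomised item**, 0.80 against 0.50, one-sided 5%, 20 patients. The documents do not give the share of positive ratings p, so 10% to 50% is an assumed range.

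Large-sample variance: var(K) = (1 − K)/N × [(1 − K)(1 − 2K) + K(2 − K)/(2p(1 − p))]. Power = Phi((0.30 − 1.645×SE0)/SE1).
- p = 0.5: SE0 = 0.194, SE1 = 0.134, power 44.5%
- p = 0.1: SE0 = 0.323, SE1 = 0.228, power 15.6%

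Two further methods were used: exact enumeration of all 2×2 tables, taking the smallest cut-off with size at most 5%, and the Donner-Eliasziw goodness-of-fit approximation.

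| Share positive | Large-sample power | Exact power | Goodness-of-fit power | N for 80%, large-sample | N for 80%, goodness-of-fit |
|---|---|---|---|---|---|
| 50% | 45% | 49% | 46% | 42 | 52 |
| 40% | 43% | 48% | – | 44 | – |
| 30% | 37% | 43% | 42% | 50 | 61 |
| 20% | 28% | 35% | 35% | 66 | 78 |
| 10% | 16% | no valid cut-off | 25% | 117 | 133 |

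Simulation at 50% positive puts the number needed for 80% at about 40.

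**4. Precision of Kappa as an estimate.** With 20 patients and an observed Kappa of 0.80, a goodness-of-fit 95% CI runs from about 0.40 to 0.94 at 50% positive and from about 0.20 to 0.97 at 10%.

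**5. Four-level Heckmatt grade.** Over 24 combinations of grade distribution, weights and disagreement model, large-sample power ranges from 17% to 82%. This supports no general statement.

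**The case against.** The strongest reply is that the analysis plan is coherent as it stands. Sections 9.3 and 9.4 turn every quantitative measure into categories, Kappa is a proper measure for those, and 9.2 already gives Bland-Altman for continuous values. A general section applies without a cross-reference. This stands. A reader might infer that the secondary outcomes require reproducibility of the continuous measurements themselves, so that naming Kappa is an error. Section 3.2 does not say so. It asks for reproducibility in the diagnosis of swallowing disorders, which classified items can serve.

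The ICC reading is also an inference, since the text says only correlation coefficient and the formula does not give exactly 20. That stands too, but the defect does not depend on it. If Pearson was meant, 9.2 plans it for association only and with no test against 0.50.

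The Kappa power figures depend on the method, on assumed frequencies, and on a test of 0.80 against 0.50 that the protocol never plans for Kappa. At 20% positive, for example, the large-sample figure is 28% and the exact one 35%. This limits the precision of the figures. It does not change their direction, because no method used brings a yes/no item above 49%.

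Finally, no decision rule depends on the reliability result. That bears on how serious the point is, not on whether the text needs correcting.

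**Conclusion.** The point holds as a mismatch between the stated sample-size justification and the planned analyses. The beta of 0.20 belongs to neither Kappa nor Bland-Altman. For Kappa on yes/no or dichotomised items, power with 20 patients is roughly 16% to 49% for 0.80 against 0.50, one-sided 5%, assuming 10% to 50% positive ratings. Even for the ICC test that appears to have been sized, power is about 75% to 77% rather than 80%.

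The mismatch itself is certain. The identification of the test as an ICC is probable, and the Kappa figures are indicative. A reader might conclude that the reliability study is invalid or that Kappa should be abandoned. The documents do not support that: Kappa on classified items and Bland-Altman on continuous values are usable as estimates, though Kappa will be imprecise. Nothing is claimed for the Heckmatt grade. The primary outcome and the 100 patients are not affected. The text should be corrected, but the consequence is confined to the reliability claims.

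**What to change.** Change Section 9.7.1 and the synopsis as follows.

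1. For the continuous measures (hyoid ascension, thickening fractions, amount and duration of lingual movement), add an ICC: two-way, absolute agreement, single measurement, with inter- and intra-examiner comparisons analysed separately. Compare its one-sided 95% lower bound with 0.50. Keep Bland-Altman as in 9.2.
2. Limit Kappa to yes/no, dichotomised and ordinal items. Use a weighted Kappa for the Heckmatt grade, with the weights stated in advance. Report 95% CIs suited to small samples and make no power claim.
3. State that the power refers to the ICC only. With 20 patients it is about 75% for the form in item 1, assuming no systematic operator difference (about 77% for a one-way ICC), and not 80%.

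An ICC of the undichotomised score may be reported as an estimate. It should carry no power claim, because the score is a weighted sum of categorical items and normal-theory power need not hold.

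The cost is a little more analysis and a slightly lower stated power. No extra patients or procedures are needed, since Section 7.2 already plans the three examinations in the first 20 patients.

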9.7.2 Validity

The threshold of the ultrasound score defining the presence of swallowing disorders will be determined using Receiver Operating Characteristic (ROC) curve analysis.

Sensitivities, specificities, positive and negative predictive values and the diagnostic Odd ratio will be calculated to determine the diagnostic accuracy of the score.

10 Expected results in terms of scientific and professional advances

This study will allow the construction and evaluation of the reliability and validity of a new ultrasound score in the diagnosis of swallowing disorders. To our knowledge, no study has evaluated the performance of an ultrasound score in the diagnosis of swallowing disorders.

The analysis of the different structures involved in swallowing will also provide knowledge on the impairment of the functions and structures involved in swallowing. This may allow to better orientate the therapeutic strategy, both medical and rehabilitation.

Moreover, as the ultrasound examination is non-invasive, non-irradiating, can be performed in a simple consultation room and requires minimal cooperation from the patient, it could be an alternative to videofluoroscopy, currently the reference examination.

Swallowing ultrasound could thus also be a tool for monitoring the effectiveness of the treatments implemented, since it can be performed frequently without adverse effects.

The results of this study will only be applicable to a population of patients consulting a day hospital for suspected swallowing disorders, mostly related to ENT surgery or a prolonged stay in an intensive care unit. Further multicentre work and in other population categories to improve external validity.

11 Expected benefits and risks for patients

